### 8.1 Inclusion Criteria

Written informed consent must be obtained before any study specific assessment is performed. Upon signing informed consent, the subject is considered enrolled in the study.

Subjects eligible for inclusion in this study must fulfill **all** of the following criteria: Among the criteria listed below, ocular criteria relates to the study eye only.

1. Adults, 20 years of age or older at the time of informed consent for participating in this study, of either gender, Japanese patient diagnosed with age-related cataract.
2. Planned routine cataract surgery (need determined by the expert opinion of the investigator).
3. Eligible to be implanted with the TFNT20 as determined by a new Alcon Toric calculator in at least one eye that incorporates ocular trends in surgical planning.
4. To qualify for fellow eye implant with TFNT20, subject must have no clinically significant findings at the Visit 1 examination of the first implanted eye.

Note: This criterion only applies to subjects who are eligible for both eyes and wishes to be implanted into fellow eye with TFNT20.

5. Willing and able to complete all required postoperative visits.
6. Subjects for able to comprehend and sign the informed consent form for participating in this study.  
For the subjects who are eligible for both eyes and wishes to be implanted into fellow eye with TFNT20, subject has to comprehend and sign the informed consent form for the second eye surgery and the study examinations prior to the examinations at Visit 0A.
7. Clear intraocular media other than cataract.
8. Subjects for whom postoperative emmetropia is planned (spherical equivalent  $\pm$  0.50 D).
9. Potential postoperative BCDVA of 0.5 decimal or better.

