### **10.1.2 Surgery Day (Visit 00/00A)**

Record surgical information at Visit 00/00A. If subjects wish to be implanted into both eyes with TFNT20, obtain consent in continuation of the study from each subject prior to the surgery on the 2nd eye.

- Operative eye  
Indicate which eye is being implanted.
- Exclusion criteria during surgery  
Assess qualification according to the inclusion/exclusion criteria during the surgery. The incision site for this study is defined as temporal ( $\pm 15^\circ$ , or approximately 1 mm, for the horizontal meridian (OS:  $0^\circ$ , OD:  $180^\circ$ )).
- Final incision size  
Indicate final incision size (mm) to the nearest 0.1 mm.
- Problems during surgery

Indicate what problems, if any, occurred during surgery. If any exclusion criteria occur, discontinue the subject from the clinical study.

[figure not shown]
- Other procedures at this surgery  
Any other procedures performed at this surgery should be indicated. Since other procedures at this surgery are included in the exclusion criteria, discontinue the subject from the clinical study.
- Lens information  
Provide the IOL information (IOL model, refractive power, serial No.) also in the event of discontinuation of implant. Attach the adhesive label contained in the package of the investigational lens to the Study Participants Card.
- IOL axis orientation (dilated)  
Record the orientation (in degrees; 0 ~180 degrees) of the investigational lens axis (designated by indentations on the IOL optic). [REDACTED]  
[REDACTED]
- Medical history  
Confirm systemic and ophthalmologic complication, ophthalmologic surgical history.
- Concomitant medications  
Indicate the concomitant ocular medications used during the surgery.
- IOL observation  
Observe the IOL surface and the inside of the haptic and optic of the investigational lens with a slit-lamp microscope, and record the presence/absence of visible abnormal findings (debris on IOL surface, forceps marks on IOL surface, IOL discoloration, IOL opacities, IOL scratch, membrane generated on IOL, pigmentation on IOL, surface haze, other.). And regarding the observed findings, evaluate the clinical significance. If the problem may negatively affect postoperative visual acuity, etc., handle it as the clinical significant, and if possible, take photos.
- Adverse events, Device deficiencies  
Presence/absence of adverse events and device deficiencies are recorded since informed consent.
- Secondary surgical intervention

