#### 12.4.1.1 Statistical Hypotheses

The primary analysis will be performed using an exact test of binomial proportion (one-sided alpha = 2.5%). The null ( $H_0$ ) and alternative ( $H_1$ ) hypotheses are;

$$H_0: \pi(T2) = 29.2\%$$

$$H_1: \pi(T2) > 29.2\%$$

, where  $\pi(T2)$  is the population proportion of eyes with  $\leq 0.25$  D refractive cylinder at Visit 3/3A (Day 30-60) for T2 group. The 29.2% is the percentage of non-Toric (T0, hereafter) group estimated from historically combined studies [REDACTED] that would have qualified for T2 according to the new Alcon Toric calculator that incorporates ocular trends in Toric IOL planning.

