## 12.8 Sample Size Justification

To enroll more than or equal to 30 eligible T2 eyes used for analysis, at least 30 subjects will be evaluated by a new Alcon Toric calculator that incorporates ocular trends in Toric IOL planning and unilaterally or bilaterally implanted with the AcrySof IQ PanOptix IOL (TFNT20).

Using a new Alcon calculator that incorporates ocular trends in Toric IOL planning, percentage of eyes with  $\leq 0.25$  D refractive cylinder at Visit 3/3A (Day 30-60) in T2 group was estimated as 60.9% based on a previous [REDACTED] (T2) study conducted in US. Using the same calculator, the percentage in T0 group was recalculated as 29.2% from the combined result of studies (non-Toric T0 lenses) conducted in Japan [REDACTED] [REDACTED]. Statistical test will be conducted to compare percentage of T2 with a constant of 29.2% as percentage of T0. With 30 eyes from 30 subjects in T2 group, assuming the percentage of T2 is equal to 60.9% [REDACTED], the statistical power to demonstrate superiority of T2 to T0 is 91.6% with one-sided alpha of 2.5%, using an exact test of binomial proportion.

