4.3 Statistical Methods for Efficacy Analyses

All eligible eyes will be used for the analysis. For unilaterally implanted subjects, only the eligible eye, for bilaterally implanted subjects, both eyes will be used for the analysis. The superiority of T2 to T0 regarding refractive cylinder is to be demonstrated when there is a statistically significant difference between the outcome in this study and the historical threshold of 29.2%. [REDACTED]

Secondary effectiveness variables [REDACTED] will be summarized descriptively. For continuous variables, descriptive statistics (mean, standard deviation, N, median, min and max) will be provided for actual value and change from baseline at each visit. For categorical variables, N and percent will be provided for each category at each visit. Any additional p-values from t-statistics or chi-square type statistics will be provided accordingly only for descriptive purpose. Also, a patient data listings will be provided for all effectiveness analysis data with all eyes at all visits.

Table 4-1 summarizes the key efficacy analyses.

Table 4-1 Summary of Analysis Strategy for Key Efficacy Endpoints

[figure not shown]
Endpoint	Main [REDACTED] Approach ^a	Statistical Method	Analysis Set	Missing Data Approach
Primary				
Percentage of eyes with ≤ 0.25 D refractive cylinder at Visit 3/3A	M	Exact test of binomial proportion	AAS	Observed data only

Secondary				
Percentage of eyes with ≤ 0.5 D refractive cylinder at Visit 3/3A	M	Descriptive statistics	AAS	Observed data only

Average manifest refractive cylinder at Visit 3/3A	M	Descriptive statistics	AAS	Observed data only
--	---	------------------------	-----	--------------------

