5.3.1 Adverse events including secondary surgical intervention (SSI)

The number and percentage of eyes with ocular adverse events (including secondary surgical interventions not-related to the optical properties of the IOL) will be presented. Also, the number and percentage of subjects with non-ocular adverse events will be presented. An eye with multiple ocular AEs of the same preferred term is only counted once toward the total of this preferred term.

Adverse events will be summarized in the following tables:

- All Adverse Events (Serious and Non-Serious Combined)
 - Ocular
 - Non-Ocular
- All Adverse Device Effects
 - Ocular
 - Non-Ocular
- All Serious Adverse Events (including Serious Adverse Device Effects)
 - Ocular
 - Non-Ocular
- Subject data Listings
 - Non-Serious Ocular
 - Non-Serious Non-Ocular
 - Serious Ocular
 - Serious Non-Ocular

Also, a patient listing will be provided for adverse experiences occurred from informed consent to exposure to the test article.

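### Whether a subject contributes one eye or two can depend on how the first eye did, and the primary test counts both eyes as independent, so one-sided 2.5% is not assured

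*Protocol*

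**What the plan says.** Under Protocol 8.1, criterion 4, to qualify for the second implant the "subject must have no clinically significant findings at the Visit 1 examination of the first implanted eye". The note beneath it limits the criterion to subjects who are eligible in both eyes and wish for the second lens. Section 10.1.2 adds that sites must "obtain consent in continuation of the study from each subject prior to the surgery on the 2nd eye". Visit 1 is at Day 1-2; the primary endpoint, refractive cylinder of 0.25 D or less, is read at Day 30-60.

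Protocol 12.4.1.2 and SAP 4.3 state that "for bilaterally implanted subjects, both eyes will be used for the analysis". Table 4-1 of the SAP assigns the exact binomial test to the All-Implanted Analysis Set, which is defined by eye. For safety, SAP 5.3.1 reports "The number and percentage of eyes with ocular adverse events".

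The sizing uses another unit. Protocol 12.8 computes power "With 30 eyes from 30 subjects in T2 group" and says: "Statistical test will be conducted to compare percentage of T2 with a constant of 29.2% as percentage of T0".

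Protocol 9.3 also matters. When both eyes qualify, the eye with the smaller anticipated residual astigmatism is operated first and the eye with the larger is second.

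**The concern.** The exact binomial test needs independent units and a number of units that carries no information about the outcome. Neither is secured here. Two eyes of one person share anatomy, surgeon and biometry, so their residual cylinder is likely to be correlated. Subjects contribute a second eye only after the first has met the Visit 1 condition and they choose to go on, so the number of eyes may depend on how the first eye did.

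The two problems call for different remedies. A cluster-robust variance around the same pooled proportion would address the correlation but not an outcome-dependent number of eyes. At stake is the error rate of the study's only confirmatory test. To a lesser degree, so is the reading of ocular AE percentages, whose denominator gains second eyes only from subjects whose first eye was clean at Day 1-2.

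**Working it through.** **Inputs from the documents** (Protocol 12.4.1.1 and 12.8): null rate 29.2%, assumed TFNT20 rate 60.9%, 30 eyes from 30 subjects, exact one-sided test at 2.5%, stated power 91.6%.

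**Assumed, because the documents give no values:** true success p = 0.292 in every eye unless stated; correlation ρ between the yes/no outcomes of fellow eyes; second-eye uptake *a* after a first-eye success and *b* after a failure; 30 subjects.

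**Step 1: the plan's own figure, one eye per subject.** With n = 30 and rate 0.292, P(X ≥ 14) = 3.21% and P(X ≥ 15) = 1.31%, so the test rejects at 15 or more. At 0.609, P(X ≥ 15) = 91.9%. This agrees with the stated 91.6% to within 0.3 points.

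**Step 2: the planned pooled test under the null.** Let s = P(second succeeds | first succeeded) = p + ρ(1−p), and f = P(second succeeds | first failed) = p(1−ρ). At ρ = 0.5, s = 0.646 and f = 0.146. Each subject yields:
- one eye: a success with probability p(1−a), a failure with (1−p)(1−b);
- two eyes: two successes with pas, one with pa(1−s) + (1−p)bf, none with (1−p)b(1−f).

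Convolving this over 30 subjects gives the joint distribution of eyes and successes. Applying the exact test's critical count at each total (for example 20 of 45, 23 of 54, 26 of 60) gives the rejection rate.

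| Uptake after success / failure | ρ = 0 | ρ = 0.3 | ρ = 0.5 |
|---|---|---|---|
| No second eyes | 1.3% | 1.3% | 1.3% |
| 50% / 50% | 1.7% | 2.7% | 3.4% |
| 72.9% / 72.9% | 1.9% | 3.2% | 4.1% |
| 100% / 100% | 1.4% | 2.7% | 3.6% |
| 80% / 70% | 1.9% | 3.7% | 5.0% |

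The 72.9% row has the same expected number of second eyes as 80%/70%: 0.292×0.8 + 0.708×0.7 = 0.729. At ρ = 0.5 the mild link therefore adds about 0.9 points, and correlation accounts for most of the excess. Here ρ is on the yes/no scale. A correlation of 0.5 on an underlying normal scale is weaker: with all subjects bilateral, simulation gives 2.7%, and 4.1% at 0.8.

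**Step 3: direction of any bias.** The expected pooled rate is (p + pas + (1−p)bf) / (1 + pa + (1−p)b). For 80%/70% and ρ = 0.5 this is (0.292 + 0.1509 + 0.0724) / 1.7292 = 29.8%, up 0.6 points. If second eyes are 5 points worse, as section 9.3 could produce, subtract 0.05 × 0.7292/1.7292 = 2.1 points. The pooled rate becomes 27.7%, below the null rate, and rejection is 2.7%. The sign depends on which effect is larger.

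**Step 4: ocular AEs.** Assume a true rate of 10% per eye, with every subject whose first eye is free of AEs receiving a second lens. With q the second eye's AE rate among those subjects, the pooled percentage is (0.10 + 0.90q) / 1.90. At an underlying correlation of 0.5, q = 0.0751 and the result is 8.8%. At 0, 0.3 and 0.8 it is 10.0%, 9.4% and 7.6%. This overstates the effect, since it treats every first-eye AE as visible by Visit 1.

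**The case against.** **The Visit 1 condition is not the endpoint.** It is a Day 1-2 clinical finding. The protocol attaches clinical significance to the slit lamp, fundus, capsule opacification and IOL observations, and nowhere to residual cylinder. This stands, and it limits the selection effect. A reader might infer a large inflation: with uptake of 80% after success and 30% after failure, and ρ = 0.5, the pooled rate is 32.8% and rejection about 8.7%. But that makes uptake depend directly on Day 30-60 success. If the Visit 1 condition alone caused the contrast, it would turn away 62.5% of eventual failures, or 0.625 × 0.708 = 44% of all subjects. The 80%/70% case needs 0.125 × 0.708, about 9%. Nothing in the documents supports the stronger figure.

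**A first-eye test has its own selection.** Section 9.3 makes the first eye the favoured one when both qualify. This stands in part. Suppose all subjects are bilaterally eligible, the average eye is at 29.2%, and uptake is unrelated to outcome. With a 5-point gap between eyes (first eye 31.7%), the first-eye test rejects 2.8% of the time; the pooled test at ρ = 0.5 rejects 4.2%, 4.6% and 3.6% at 50%, 80% and full uptake. With a 10-point gap (first eye 34.2%), the first-eye test rejects 5.4% against 5.2%, 4.8% and 3.5%. So the first-eye test compares well unless the gap is large, and the selection must be disclosed.

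**The AE effect is conditional.** It vanishes if eyes are independent, safety is descriptive, and subject listings are planned. That is fair; the request is only for clearer tables.

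**Redaction.** Text in SAP 4.3 and part of a Table 4-1 column header are blacked out, so a sensitivity analysis may exist. The readable main analysis still pools eyes.

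**Conclusion.** The concern holds as a question of error control and analysis unit. The plan sizes on one eye per subject, tests up to two as independent, and lets the number of eyes depend on the first eye's Visit 1 result and the subject's wish. Under assumed yes/no correlation of 0.5 and equal success in both eyes, rejection under the null is about 3.4% to 4.1% with uptake unrelated to outcome and about 5% with a mild link, against 1.3% for first eyes only. If eyes are independent, it remains below 2.5%.

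A reader might conclude that pooling must push the success percentage up. The documents do not support that: the Visit 1 condition is not cylinder, and section 9.3 places the eye expected to do worse second. Net direction and size are unknown. Dilution of per-eye AE percentages is possible but needs within-subject correlation. All correlation, uptake and gap values are assumptions.

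**What to change.** In Protocol 12.4.1.2 and SAP 4.3, run the primary exact test on the first implanted eye of each subject. Report second eyes, and all eyes pooled, as supportive. With 30 subjects the rule is to reject at 15 or more. State beside the result that, where both eyes qualify, section 9.3 chooses the first eye for its smaller anticipated residual astigmatism, so the conclusion applies to first eyes and should be read next to the all-eyes figure.

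In SAP 5.3.1, add ocular AEs by first and second eye, and the number of subjects with at least one ocular AE, next to the pooled per-eye table.

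The fellow-eye criterion is unchanged. The cost is wording in both documents and some extra table columns. Second eyes no longer add to the confirmatory sample, but the stated power never counted them.

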## **8.2 Exclusion Criteria Prior to Cataract Surgery**

Subjects fulfilling **any** of the following criteria are not eligible for participation in this study. Among the criteria listed below, ocular criteria relates to the study eye only.

1. Any disease or pathology, other than cataract, that (in the expert opinion of the investigator) is expected to reduce the postoperative BCDVA to a level worse than 0.5 decimal
2. Prior retinal detachment.
3. Irregular corneal astigmatism as assessed by topographer per investigator decision.
4. Pregnancy or lactation, current or planned, during the course of the study.
5. Participation in another concurrent clinical trial.
6. Pupil less than 6mm after dilation.
7. History of anterior segment (corneal, anterior chamber, sulcus) or posterior segment (uveal, vitreo-retinal) pathology including retinal vascular occlusive disease, retinal detachment or peripheral retinal laser photocoagulation, ARMD, glaucoma

(uncontrolled or controlled with medication) or ocular hypertension, diabetic retinopathy, retinitis pigmentosa and any optic nerve pathology.

8. History of previous intraocular or corneal (refractive or trauma related) surgery.
9. Any other planned ocular surgical procedures including but not limited to LRI/Astigmatic Keratotomy and LASIK
10. Subjects with conditions that increase the risk of zonular rupture during cataract extraction procedure that may affect the postoperative centration or tilt of the IOL.
11. Presence or history of any condition or finding that makes the subject unsuitable as a candidate for cataract surgery or study participation or may confound the outcome of the study, in the opinion of the Investigator.

### **8.3 Exclusion Criteria During Cataract Surgery**

The patient who meets any criteria specified in the following 1) through 9).

1. Any other additional procedures during the cataract removal and IOL implant due to intraoperative complications that require further intervention (including but not limited to posterior capsule rupture, with vitreous loss, zonular dehiscence that may make the IOL implant less stable, etc.).
2. Mechanical or surgical intervention required to manipulate the pupil.
3. Excessive iris mobility.
4. Significant vitreous loss.
5. Significant anterior chamber hyphema.
6. Zonular or capsular rupture.
7. Unrecognized (pre-existing but discovered during surgery) ocular conditions or complications in which the IOL stability could be compromised, including zonular weakness.
8. Haptic placement other than bag-bag.
9. Incision other than temporal location

## **8.4 Rescreening of Subjects**

Rescreening of subjects is not allowed in this study.

## 9 TREATMENTS ADMINISTERED

### 9.1 Investigational Product(s)

*Test Product(s):* TFNT20

*Control Product(s) (If applicable):* Not applicable

**Table 9–1 Test Product**

Test Product	TFNT20
Indication for use and intended purpose in the current study	The TFNT20 is intended for primary implantation in the capsular bag in the posterior chamber of the human eye for the visual correction of aphakia and pre-existing corneal astigmatism, secondary to removal of a cataractous lens in adult patients who desire near, intermediate, and distance vision with increased spectacle independence.
Product description and parameters available for this study	
Single-piece construction lens consisting of the optic and the haptic made of the same material. The optic diffractive structure is in the central 4.5 mm portion of the optic zone (6.0mm), overall length: 13.0 mm, on the anterior surface and divides the incoming light to create a +2.17 D intermediate and a +3.25 D near add power. The posterior surface of Model TFNT20 is toric, and is designed with 1.00 D of cylinder power (0.68 D at the corneal plane in an average pseudophakic human eye ). The flat meridian of the AcrySof IQ PanOptix Toric IOL is identified with the indentations on the posterior surface of the optic in the form of dots.
 
The details of the test product can be found in the Investigator’s Brochure (#IB-0175).

Formulation	Not applicable.

Usage	The investigational product will be placed within the capsular bag after removal of the natural crystalline lens following phacoemulsification.
Packaging description	Pack each test product into the carton.
Labeling description	
The carton with labeling of:
 

• Name and address of the Sponsor

• Purpose (for use in clinical study)

• Lens model, serial number and refractive power, A-constant

• Method of storage and precautions

 
The package contains the following adhesive labels besides the test products:
 

• Investigational lens control labels (to be attached to Investigational lens Control Log, medical record)

• Copy of the investigational lens information given to study subjects (to be attached to the Study Participants Card).

Storage conditions	Keep the lens not at a high temperature/humidity and away from direct light. Do not keep the lens at 45°C or higher.
Supply	Refer to the management manual of test product for a detailed description.

The TFNT20 must be maintained within specified environmental condition, per the labeling.

A temperature log must be maintained documenting appropriate IP storage conditions as described in the management manual of test product, and must be made available for inspection.

More information on the test product can be found in the Investigator's Brochure (#IB-0175) and management manual of test product.

## **9.2 Other Medical Device or Medication Specified for Use During the Study**

No other medical devices or medications are required to be used in conjunction with the treatments during the clinical study.

## **9.3 Treatment Assignment / Randomization**

Only after signing the ICF, a subject will be assigned a subject number by the electronic data capture system.

The investigational product will be placed within the capsular bag after removal of the natural crystalline lens. When both eyes are eligible, the eye which has smaller anticipated residual refractive astigmatism based on a new Alcon Toric calculator that incorporates ocular trends in Toric IOL planning shall be the first eye, and the eye which has larger anticipated residual refractive astigmatism shall be the second eye. If both eyes have same anticipated residual refractive astigmatism, the eye with advanced cataract shall be the first eye and the fellow eye should be the second eye.

## **9.4 Accountability Procedures**

Upon receipt of IPs, the Investigator or delegate must conduct an inventory of the test product by serial number, complete study-specific confirmation of receipt procedures as described in the management manual of test product , and retain any required documentation in the Investigator's clinical study records. Throughout the study, the Investigator or delegate must maintain records of IP dispensation for each subject. This record must be made available to the study monitor for the purposes of verifying the accounting of IP supplies. Any discrepancies and/or deficiencies between the observed disposition and the written account must be recorded along with an explanation. All IPs sent to the Investigator must be accounted for by Study Sponsor personnel, and in no case be used in an unauthorized manner.

- Return to the Study Sponsor investigational products associated with a device deficiency. Refer to Section 11 of this protocol for additional information on the reporting of device deficiencies and to the management manual of test product for information on return of study products associated with these events.

The Investigator is responsible for proper disposition of all unused IPs at the conclusion of the study, according to the instructions provided in the management manual of test product.

